6.3. Study Rationale

Currently, no published studies on the comparative effectiveness or cardiovascular safety of ABL versus TPTD in a real-world setting are available ([Fuggle et al, 2020](#)). There are also no real-world data on the cardiovascular safety of these osteoanabolic agents in this patient population. In an earlier study, Radius used data from claims and electronic medical records to characterize patients new to ABL relative to patients new to TPTD. Results from that study were previously reported and the differences in patient characteristics in the real-world setting were noted when compared with the characteristics of patients in clinical studies ([Imel et al, 2020](#)). Furthermore, patients new to ABL treatment were similar in their disease characteristics to patients on TPTD. This observation reflects comparable market access to the 2 anabolic therapies in addition to an equivalence in prescribing recommendations based on clinical practice guidelines ([Camacho et al, 2020](#)).

Previously, Radius completed an analysis of Symphony Health Patient Source administrative claims data for evaluation of the market dynamics for osteoporosis treatments ([Williams et al, 2019](#)). The purpose of that study was to characterize patients new to anabolic treatment in the real-world setting and to evaluate incidence of fractures following treatment initiation. Baseline cardiovascular risk factors (ie, dyslipidemia, hypertension, diabetes, and obesity), disease history and cardiovascular events before and after treatment initiation were evaluated as exploratory analyses. Because the study started shortly after the launch of ABL (TYMLOS), limited longitudinal data were available to assess impact of treatment on fracture outcomes. Furthermore, the data capture rate for inpatient events was low (only 25% of inpatient events were captured). The current protocol incorporates the recommendations received from several national scientific advisory meetings in the EU to expand data scope and further evaluate the real-world comparative effectiveness and comparative cardiovascular safety of ABL versus TPTD. First, additional real-world data have been accumulated leading to a larger number of evaluable patients with a longer longitudinal data availability. Second, we have secured access to the enhanced hospital data through PRA Health Sciences, which provide access to 60% of inpatient events. Furthermore, mortality data, which were previously not available, can now be determined using hospital discharge records. A validated cardiovascular mortality algorithm ([Xie et al, 2018](#)) will be used to derive in-hospital cardiovascular mortality. Both in-hospital cardiovascular mortality and all-causes mortality will be included.

The purpose of the current study is to evaluate the real-world comparative effectiveness and comparative cardiovascular safety of ABL versus TPTD during the 18-month period after treatment initiation in PS matched cohorts.

[figure not shown]
This study will be conducted by PRA Health Sciences using this prespecified protocol and statistical analysis plan. In the absence of randomization, this observational study will use propensity score (PS) matching for comparative evaluation of safety in addition to effectiveness outcomes. Further quality control work has been performed on the data including the assignment of codes. The study has reasonable power to show comparable effectiveness and safety profile between the 2 active treatment arms.

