6.2.3. Abaloparatide

Abaloparatide is a chemically synthesized analog of the first 34 amino acids of human parathyroid hormone-related peptide [hPTHrP(1-34)] that is anabolic in bone. Secondary pharmacological effects of ABL include transient and reversible increases in heart rate after injection, with associated AEs of palpitations and tachycardia observed in the pivotal clinical study. A post-hoc analysis was performed to examine the effects of treatment on heart rate, blood pressure, and cardiovascular-related AEs, including MACE with or without heart failure in the ACTIVE/ACTIVExtend study ([Cosman et al, 2020](#)). ABL and TPTD transiently increased heart rate relative to placebo. After the first dose, the mean (SD) change in heart rate from before treatment to 1 hour after treatment was 7.9 (8.5) bpm for ABL, 5.3 (7.5) bpm for TPTD, and 1.2 (7.1) bpm for placebo. A similar pattern was observed over subsequent visits. The corresponding change in mean supine systolic and diastolic blood pressure 1 hour after treatment was -2.7/-3.6 mmHg for ABL, -2.0/-3.6 mmHg for TPTD, and -1.5/-2.3 mmHg for placebo. The percentage of participants with serious cardiac AEs was similar across the treatment groups (0.9% and 1.0%). In a post-hoc analysis, the percentage of participants with MACE during the ACTIVE study was 0.5% in the ABL group, 0.6% in the TPTD group, and 1.2% in the placebo group; MACE + heart failure increased the proportion in the placebo group to 1.7%. Time-to-first incidence of MACE + heart failure was significantly longer for ABL compared with placebo ($p = 0.02$) and for TPTD compared with placebo ($p = 0.04$; [Cosman et al, 2020](#)). During the 2-year ACTIVExtend period, the incidence of MACE, with or without heart failure, was similar between the placebo/alendronate and ABL/alendronate groups leading to the conclusion that ABL was associated with transient increases in heart rate and small decreases in blood pressure in postmenopausal women with osteoporosis, with no increase in risk of serious cardiac AEs, MACE, or heart failure.

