7.8.1.2. Power Calculation

- Abaloparatide versus teriparatide with a noninferiority margin of 30%
 - Assuming a nonvertebral fracture rate of 3.5% at the end of 18 months
 - 8,000 matched subjects in each group
 - 95% power for HR up to 1.3

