7.8.6. Effectiveness Analyses

In this study, the primary analyses of effectiveness will be noninferiority analyses for ABL versus TPTD on time to the first incidence of nonvertebral fractures with a margin of 30%. Noninferiority of ABL to TPTD will be concluded if the upper bound of 2-sided 95% CI of HR between ABL versus TPTD is < 1.3.

In a recently published historical control observational study evaluating the real-world effectiveness of osteoporosis therapies using Medicare claim data between 2008 and 2011, the fracture incidence rates for the 12-month pre-treatment period were compared with the 12-month on-treatment period ([Yusuf et al, 2018](#)). For patients treated with TPTD, the incidence rate ratio (IRR [95% CI]) was 0.36 (0.31 to 0.41) for any fracture and 0.34 (0.32 to 0.36) for hip fracture. Based on the EMA and FDA noninferiority margin guidelines ([EMA, 2005](#); [FDA, 2016](#)), if the upper boundary of ABL versus TPTD is $HR < 1.3$, then ABL will preserve approximately 70% of the TPTD benefit, which is higher than the minimum required threshold of 50%.

Comparisons of the time to fracture between the PS-matched ABL and TPTD groups will be based on a Cox proportional hazards model. The hazard ratio (HR) and 95% confidence interval (CI) between the 2 treatment groups will be calculated. The Kaplan-Meier method will be used to estimate event rates. Log rank test will be calculated.

For the fracture outcomes, and the corresponding sensitivity and subgroup analyses, patients will be followed for up to 18 months or until their first fracture event (for the fracture site of interest under evaluation), whichever comes first. All analyses are based on index medication cohort.

The duration, in days, from the date of the first filled prescription for ABL or TPTD to the first incidence of nonvertebral fracture will be derived. If a patient does not experience any nonvertebral fractures during the 18 months of treatment + 30-day follow-up (for a total of 19 months), the patient will be censored at the day of in-hospital death or the 19 months.

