7.8.7. Safety Analyses

A Cox proportional hazards model will be used for the time to first cardiovascular event. HR and 95% CIs will be presented.

The ICD-10 diagnosis from the hospital claim and physician claim will be used to derive post-index myocardial infarction (MI) (I21.x, I22.x), stroke (I61.x – I63.x), or heart failure (I50.x, excluding I50.x2, I50.8x). Hospital discharge status code (20 to 29 or 40 to 42) will be derived for in-hospital death. A detailed code list is provided in [Appendix 3](#). Subjects with in-hospital cardiovascular death derived from indirect approach 2 ([Xie et al, 2018](#)) will be included in the analyses. 2018 ICD-10 CM and General Equivalence Mappings (GEMS) from the Centers for Medicare & Medicaid (CMS) ([will be used to translating ICD-9 CM to ICD-10 CM \(CMS, 2018\)](#)).

The As-Treated (AT) analysis will be conducted for the safety evaluation. The first incidence of a cardiovascular event after the index date and before the 30 days after the end of treatment will be analyzed.

A cardiovascular event is the first incidence of the composite endpoint of nonfatal MI, nonfatal stroke, or in-hospital cardiovascular death; the first incidence of the composite incidence of nonfatal MI, nonfatal stroke, heart failure or in-hospital cardiovascular death; or the first incidence of MI, stroke, heart failure, or in-hospital cardiovascular death separately.

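### The rationale claims power to show a comparable safety profile, but the plan gives no cardiovascular event rate, event count, margin or power to support it

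*Combined protocol and SAP*

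**What the plan says.** Section 6.3 closes with an unqualified statement: "The study has reasonable power to show comparable effectiveness and safety profile between the 2 active treatment arms".

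Section 7.8.1.2 is the only place where power is calculated. Its inputs are a 30% margin, a fracture rate ("Assuming a nonvertebral fracture rate of 3.5% at the end of 18 months") and "8,000 matched subjects in each group". Its result is "95% power for HR up to 1.3". Section 7.8.6 gives the matching decision rule, again for nonvertebral fracture: noninferiority is concluded "if the upper bound of 2-sided 95% CI of HR between ABL versus TPTD is < 1.3".

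For the CV endpoints, section 7.8.7 specifies a Cox model and says only that "HR and 95% CIs will be presented". The synopsis adds Kaplan-Meier estimates and a log-rank p-value. Neither sets a threshold.

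The only on-drug MACE figures are in the background, section 6.2.3, from a post-hoc analysis: "the percentage of participants with MACE during the ACTIVE study was 0.5% in the ABL group, 0.6% in the TPTD group". For MACE plus heart failure, that section gives a percentage for placebo only.

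**The concern.** Cardiovascular safety is the secondary objective and half of the study's stated purpose. A claim that the design has reasonable power to show comparable safety needs two things: a definition of comparable, and an expected number of events. The plan has both for fracture and neither for CV events.

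The gap matters because MACE may be much rarer than fracture in this population, so the sample size that serves the primary endpoint need not serve this one. With no criterion fixed in advance, a wide interval around 1 or a non-significant log-rank test could be read as evidence of comparability on the strength of the sentence in 6.3.

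**Working it through.** **Inputs.** 8,000 per arm, 3.5% fracture at 18 months, margin 1.3 (7.8.1.2); two-sided 95% CI (7.8.6); MACE 0.5% and 0.6% in ACTIVE (6.2.3). The 1.5 threshold is used here for illustration. The value 1.3 is the fracture margin, borrowed because it is the only one in the plan. Neither is a CV criterion in the document.

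**The plan's own figure.** The stated 95% is for fracture. It reproduces on the risk-difference scale: margin 0.30 × 3.5% = 1.05 percentage points; SE = sqrt(2 × 0.035 × 0.965 / 8,000) = 0.00291; Φ(0.0105/0.00291 − 1.96) = 95%. On the HR scale, with 2 × 8,000 × 0.035 = 560 events, a true HR of 1 and the two-sided 95% CI, it is Φ(ln 1.3 / (2/√560) − 1.96) = 87%. That difference is a side matter. Either way, the figure rests on about 560 fractures and says nothing about CV events.

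**CV events at the ACTIVE rates.** 8,000 × 0.005 + 8,000 × 0.006 = 40 + 48 = 88, if every woman is observed on drug for 18 months and every event is captured.

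**Precision at a true HR of 1.** SE(log HR) = 2/√events; expected upper limit = exp(1.96 × SE); chance of excluding a ratio m = Φ(ln m / SE − 1.96). The incidences of 0.3%, 1% and 2% are assumptions.

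| Incidence on treatment | Events in 16,000 | SE | Expected upper limit | Chance of excluding 1.5 | Chance of excluding 1.3 |
|---|---|---|---|---|---|
| 0.3% (assumed) | 48 | 0.289 | 1.76 | 29% | 15% |
| 0.55% (mean of the two ACTIVE rates) | 88 | 0.213 | 1.52 | 48% | 23% |
| 1% (assumed) | 160 | 0.158 | 1.36 | 73% | 38% |
| 2% (assumed) | 320 | 0.112 | 1.24 | 95% | 65% |

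A binomial simulation at 0.55% in both arms gave 47% and 23%.

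**Precision if 0.5% versus 0.6% is the truth.** HR = 40/48 = 0.83; SE = sqrt(1/40 + 1/48) = 0.214; expected upper limit = 0.833 × exp(1.96 × 0.214) = 1.27. The chance of excluding 1.5 is Φ(ln(1.5/0.833)/0.214 − 1.96) = 78%, and of excluding 1.3 is 55%.

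**If abaloparatide raised MACE by half.** With teriparatide at 0.6%, the counts are 48 and 72; SE = sqrt(1/48 + 1/72) = 0.186; the chance of two-sided significance is Φ(ln 1.5/0.186 − 1.96) = 59%, so the chance of missing it is about 41%.

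**Events for 80% power at a true HR of 1.** 4 × (1.96 + 0.84)² / (ln m)² gives 191 events to exclude 1.5 (191/16,000 = 1.2% incidence) and 457 to exclude 1.3 (457/16,000 = 2.9%).

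**The case against.** The strongest reply is that the ACTIVE rates are not planning assumptions. They are background from a trial, and the claims cohort may have more events. Section 7.1.4 expects a population that may be less healthy, though it says so about fracture. Prior MI or stroke is not an exclusion in Table 2. The main CV analysis counts the first code after index without a washout, and section 7.8.10.2 itself raises possible overestimation. This stands: the event count could be well above 88, and at 2% the study would be informative against a 50% excess.

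The count could also be lower. CV follow-up is limited to time on therapy, section 6.3 puts access to inpatient events at 60%, and section 7.5 says that discharge status covers about a third of deaths. It would be tempting to multiply 88 by 0.6. The document does not support that, because MI, stroke and heart failure are also taken from physician claims, so overall capture cannot be read as 60%.

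Two stronger inferences also fail. A reader might conclude that the study could not exclude a 50% excess. At a true HR of 1 and 88 events, it is close to an even chance, and at 0.5% versus 0.6% as the truth, exclusion is more likely than not. A reader might also expect a non-significant result to be likely despite a true 50% excess. With 48 and 72 events, significance is the more likely outcome.

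Finally, nothing in the plan says that non-significance will be reported as comparable safety. The synopsis bases comparisons on the confidence interval, so the precision will be visible. That reduces the risk of misreading but does not supply the missing criterion.

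**Conclusion.** The point holds as a power claim that the plan does not support. The power calculation and the margin cover nonvertebral fracture only, and this conclusion depends on no assumed rate.

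The size of the shortfall does depend on the rate. At the ACTIVE rates, with full capture, 18 months on drug and a true HR of 1, about 88 events give an expected upper 95% limit near 1.52. Power is then well short of 80% for either illustrative threshold. At 1% it is still short for both; at 2% it is ample for 1.5 but not for 1.3. The document does not say which of these applies, so the claim is unsupported rather than shown to be false. The figures are for the first composite. The second, which adds heart failure, would have at least as many events, but no on-drug rate is given for it.

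**What to change.** - Section 6.3: remove safety from the power statement, or support it with a calculation that names the endpoint, the assumed rate and the ratio to be excluded.
- Sections 7.8.1.2 and 7.8.7: give the expected CV precision (event count, expected upper 95% limit, chance of excluding stated ratios) over a stated range of assumed event counts, for both composites.
- Section 7.8.7: state that the CV conclusion will be the excess risk that the upper 95% limit excludes, and that a non-significant HR or log-rank p-value will not be reported as comparable CV safety.

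The cost is wording in the protocol and SAP, with no more patients or data. The price is that the stated property of the design becomes less favourable.

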7. RESEARCH METHODS

7.1. Study Design

This will be a retrospective observational study using administrative data for the period from May 2012 to January 2021. The most recently available data at the time of data extraction will be used. This study will use anonymized patient claims data from PRA's Symphony Health Patient Source Integrated Dataverse (IDV) database with the inclusion of enhanced hospital data, which are claims and remittance from the inpatient hospital setting and proprietary Patient Transactional Dataset (PTD) claims and prescription data, to apply the inclusion/exclusion criteria for patient selection (see [Section 7.4.1](#)) to form the data set.

Figure 1 Study Design Schematic

ABL= abaloparatide; TPTD = teriparatide.

The **Identification Period** is the period of time during which subjects will be identified based on their index date (01 May 2017 to 30 June 2019).

The **Index Date** is the date on which the subject filed their first claim for a prescription for either ABL or TPTD during the identification period.

The **Pre-index Period** consists of the 5 years before the Index Date during which medical history was available for the subject.

The **Post-index Treatment Period** consists of the 18 months plus 30 days follow-up after the initiation of treatment with anabolic drug (ABL or TPTD) on the index date and continuing for the duration of treatment.

Treatment Cohorts

This is a real-world observational study. Treatments will not be assigned. Instead, cohorts are defined as follows:

- **Abaloparatide Cohort:** Patients who filled ≥ 1 prescription for ABL (TYMLOS) as their index medication during the identification period.

- **Teriparatide Cohort:** Patients who filled ≥ 1 prescription for TPTD (Forteo) as their index medication during the identification period.

Evaluation Period

The date of the first claim for either ABL or TPTD during the identification period (between May 1, 2017 and June 30, 2019) will be considered the index date.

- The medication received on the index date will be considered the index medication.
- Treatment duration may continue for up to 18 months (540 days) after the index date.
- The evaluation of outcomes will start immediately after treatment initiation and will continue for 18 months after the index date for both effectiveness and cardiovascular safety evaluation regardless of the drug possession gap between any 2 prescription fills.

Primary Analyses

- The primary effectiveness analysis will be an Intention-to-Treat (ITT) analysis.
- The primary safety analysis will be an As-Treated (AT) analysis.

Estimated Sample Size

Between May 2017 and June 2019, a total of 16,482 unique female patients ≥ 50 years of age treated with ABL and 45,350 unique patients ≥ 50 years of age treated with TPTD have been identified in the Symphony database. After applying inclusion/exclusion criteria, the final number of patients will be determined through PS matching. Based on previous studies, it is estimated that approximately 8,000 matched patients will be included in each cohort.

[figure not shown]

[figure not shown]
Sponsor Name: Radius Health, Inc.

Protocol Number: BA058-05-028

Protocol Version and Date: Original, V1.0, dated 09 July 2021

Page 27 of 63

7.1.1. Rationale for the Current Study Design

Currently, there are no published studies on the effectiveness of ABL in the real-world setting. Furthermore, neither the comparative effectiveness nor comparative safety of ABL versus TPTD have been previously reported. In addition to clinical outcomes evaluated in randomized controlled studies, real-world effectiveness data are important in guiding treatment decisions. An evaluation of real-world effectiveness will provide data on a broader population of patients beyond the patient population included in the ACTIVE trial. Romosozumab is excluded from this study because of its association with an increased risk of cardiovascular events.

7.1.2. Strengths of the Study Design

The methodology for the current study design has several strengths:

- Data are from multiple payers and geographically diverse settings across the USA, and the PRA IDV data captures over 90% of pharmacy claims in the USA. The prescription claims are for prescriptions filled not just prescriptions written. As such, the findings from the study are expected to have a high generalizability.
- A claims-based algorithm, which has a high specificity and has been shown to have over 90% accuracy in previous studies, will be used ([Wright et al, 2019](#)).
- Although this is not a randomized study, PS-matching will be used to define study cohorts and provide confidence that the 2 cohorts were comparable in their probability to receive and benefit from treatment. Patients will be matched on all indicators of disease severity and fracture risk, including fracture and treatment history as per evidence-based clinical practice guidelines (Camacho et al., 2020). Furthermore, patients will also be matched on conditions associated with increased risk of fall and the requirement for treatments associated with poor bone health or quality.

7.1.3. Limitations of the Study Design

There are several limitations associated with the design of the current study:

- The data source is administrative claims data, which are not collected for research purposes. Administrative claims data have inherent limitations including coding errors, inconsistencies, underestimation, overestimation, or incomplete diagnoses data. The current study, however, will use a claims-based algorithm to identify case qualifying (CQ) fragility fractures associated with osteoporosis. Furthermore, any misclassification of fractures is nondifferential between the treatment groups being compared and should not affect the results.
- Claims-based studies include potential inaccuracies related to the use of prescription medications. The prescription claim is for the date of first fill and not the date of first use of the medication, so the assumption is that these are the same date.

- Detailed clinical data such as BMD T-scores or the presence of other risk factors (eg, family history, smoking status, alcohol intake) associated with disease severity and increased future fracture risk are not available and, therefore, no adjustments have been made for these factors.
- Only deaths recorded on the hospital discharge status are available for the derivation of cardiovascular death in this study. The current study, however, will use a claims-based algorithm to identify deaths that are likely to be caused by cardiovascular events. Furthermore, any misclassification of deaths is nondifferential between the treatment groups being compared and should not bias the results.

The comparative evaluation of treatment options is ideally done within the controlled clinical study setting. The current study is observational, and treatments are not assigned. As such, randomization is not possible. Although this is not a randomized study, PS matching will be used to define the study cohorts and provide confidence that the 2 treatment groups are comparable in their probability to receive and benefit from treatment. Patients will be matched on all indicators of disease severity and fracture risk including prior disease and treatment history. Furthermore, patients will also be matched on history of falls as well as comorbid conditions and concomitant medications associated with increased fall risk or with bone quality and strength. While several comorbidities were initially considered, some measures were ultimately not included in the end due to lack of available data. This includes duodenitis. Lastly, there could be residual confounding despite matching. The study is planned as an intention-to-treat (ITT) analysis for effectiveness evaluation and as-treated (AT) analysis for safety evaluation with additional consideration for duration of treatment exposure using sensitivity analyses on various length of observed treatment duration for the study cohorts. Interpretation is limited by the variable length of follow-up.

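### Section 7.1.3 says nondifferential fracture misclassification is harmless, but false-positive fractures pull the HR toward 1 and so favour the noninferiority conclusion

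*Combined protocol and SAP*

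**What the plan says.** Section 7.1.3 accepts that claims data contain coding errors leading to both under- and overestimation of diagnoses. It then says of the fracture endpoint that "any misclassification of fractures is nondifferential between the treatment groups being compared and should not affect the results". Section 7.1.2 describes the fracture algorithm as highly specific and says it "has been shown to have over 90% accuracy in previous studies". Neither section gives a PPV, a sensitivity or a specificity, and accuracy is not defined.

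Under Section 7.8.6 noninferiority is concluded if the "upper bound of 2-sided 95% CI of HR between ABL versus TPTD is < 1.3". The power calculation in Section 7.8.1.2 rests on "8,000 matched subjects in each group" and on "Assuming a nonvertebral fracture rate of 3.5% at the end of 18 months".

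The sensitivity analyses in Section 7.8.10 vary the matching caliper, the length of exposure, prior denosumab or zoledronic acid use, and the cardiovascular definitions. One of them addresses possible overestimation of events, but only for MI, stroke and heart failure. None addresses misclassified fractures.

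**The concern.** Section 7.1.3 treats the word nondifferential as enough to dismiss outcome error. Whether it is enough depends on the kind of error and on the hypothesis tested. False-positive fractures arising equally in both arms add the same number of spurious events to each, so the ratio moves toward 1. In a superiority test that is conservative. In a noninferiority test it makes a truly inferior drug look closer to its comparator.

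At stake is the primary decision. If a share of the recorded fractures is false, the rule is applied to a diluted HR, and the chance of declaring noninferiority when the true HR is 1.30 exceeds the 2.5% that a two-sided 95% interval implies. As written, the plan gives readers no reason to look for this and no analysis that would show it.

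**Working it through.** **Inputs.** 8,000 per arm, a 3.5% fracture rate and a 30% margin (Section 7.8.1.2); two-sided 95% CI with limit 1.3 (Section 7.8.6), hence an implied one-sided 2.5%. At 3.5% in each arm, expected events are 2 x 8,000 x 0.035 = 560. The false-positive share f is an assumption, because the documents give none.

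**The plan's own figure.** The stated 95% power reproduces as a risk-difference calculation: margin 0.30 x 0.035 = 0.0105; SE = sqrt(2 x 0.035 x 0.965 / 8,000) = 0.00291; power = Phi(0.0105/0.00291 - 1.96) = 95.1%. On the log-HR scale of the planned Cox test, SE = 2/sqrt(560) = 0.0845 and power at HR 1 is Phi(0.2624/0.0845 - 1.96) = 87.4%. That difference is a separate matter. The log-HR scale is used below because the decision rule is stated on it.

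**False positives.** Let f be the share of recorded teriparatide-arm fractures that are false, with equal absolute false-positive rates in the two arms. Then

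observed HR = (1 - f) x true HR + f

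and at a true HR of 1.30

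false noninferiority rate = Phi((ln 1.3 - ln observed HR)/SE - 1.96).

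The SE is either 2/sqrt(560), or sqrt(1/e0 + 1/e1) with e0 = 280 and e1 = 280 x observed HR. Each range in the table spans the two.

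| f | Observed HR when true HR = 1.30 | One-sided error |
|---|---|---|
| 0 | 1.300 | 2.5% |
| 2% | 1.294 | 2.8-2.9% |
| 5% | 1.285 | 3.4-3.5% |
| 10% | 1.270 | 4.6-4.8% |
| 20% (stress case) | 1.240 | 8.1-8.5% |

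Example at f = 10%: 0.9 x 1.30 + 0.1 = 1.27; ln 1.3 - ln 1.27 = 0.02335; 0.02335/0.0845 - 1.96 = -1.68, giving 4.6%. A simulation of 200,000 replicates gave 4.8% at f = 10% and 8.6% at f = 20%.

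**Missed fractures only.** Thin the true events by sensitivity s, with no false positives. At s = 0.8 the observed HR is 1.299, the error is 2.6% and power at HR 1 falls from 87% to 79%. At s = 0.6 the figures are 1.297, 2.6% and 67%. The bias is negligible and the cost is power.

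**Does high specificity remove the problem?** Not for an outcome this rare. Treating nearly all patients as fracture-free, f is about (1 - specificity)/0.035. Per-patient specificity of 99.8% gives 0.002/0.035 = 5.7%, and 99.5% gives 0.005/0.035 = 14.3%.

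**Effect on preserved benefit.** Section 7.8.6 cites a teriparatide incidence rate ratio whose upper confidence limit is 0.41. On the log scale an upper bound of 1.30 preserves 1 - ln 1.3/ln(1/0.41) = 1 - 0.262/0.892 = 71%, in line with the plan's approximate 70%. At f = 10%, an observed bound of 1.30 corresponds to a true bound of (1.30 - 0.10)/0.90 = 1.333, which preserves 1 - 0.288/0.892 = 68%. The 50% threshold corresponds to an HR of exp(0.892/2) = 1.56.

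**The case against.** The strongest reply is that most of the error here may be under-capture. The only capture figures in the documents are for coverage: about 60% of inpatient events (Section 6.3) and about 60% of outpatient professional claims (Section 7.5). The fracture definition also limits false positives by requiring an inpatient stay, or an outpatient diagnosis with a same-day repair code (Appendix 2). This stands in part. A reader might infer that all nondifferential misclassification biases toward noninferiority; the missed-fracture calculation shows that it does not. False positives remain possible, however. An inpatient diagnosis counts in any claim position, and the algorithm was validated on ICD-9 codes (Section 7.6.7.1), while all outcomes fall in the ICD-10 period.

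Second, no size can be read from the documents. The accuracy statement in Section 7.1.2 is not a PPV, and even if it were read as one, more than 90% would exclude the 20% row. This stands: the direction is firm, the magnitude is assumed.

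Third, the dilution formula depends on its conditions. If PPV were the same in both arms, true events would be the same fraction of recorded events in each, and the HR would need no correction. This also stands, and any bias analysis must say so.

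Fourth, the historical teriparatide effect behind the margin also comes from claims data and may itself be diluted. The documents do not settle this, so it should not be claimed that a diluted HR is being set against an undiluted margin. The error rate at a true HR of 1.30 is affected either way.

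Finally, a reader might extend the point to deaths, where Section 7.1.3 says that "any misclassification of deaths is nondifferential between the treatment groups being compared and should not bias the results". The documents do not support that extension. The safety analyses set no noninferiority margin, so there is no corresponding error rate to inflate. The stated limitation is that only in-hospital deaths are available, about a third of death records by Section 7.5. Section 7.8.10.2 already substitutes all-cause in-hospital death as a sensitivity analysis.

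**Conclusion.** The sentence in Section 7.1.3 is wrong as it applies to false-positive fractures under the Section 7.8.6 rule. With equal absolute false-positive rates in both arms, any f above zero moves a true HR of 1.30 toward 1 and raises the one-sided error above the implied 2.5%: slightly at f = 2%, and to nearly twice the nominal level at f = 10%. These sizes assume 8,000 per arm, a 3.5% recorded rate and a given f; the documents fix the first two as planning values and not the third.

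A reader might infer that the preserved-benefit argument fails. It does not: a true bound of 1.333 still preserves about 68% against the plan's 50% threshold. What is weakened is the claim to have met the 1.3 criterion at the implied error rate.

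**What to change.** In Section 7.1.3, replace the fracture sentence with: *False-positive fractures, even if nondifferential, bias the HR toward 1 and favour noninferiority; missed fractures mainly reduce power.*

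Add to Section 7.8.10 a prespecified quantitative bias analysis of the primary endpoint:

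HR_corrected = (HR_obs - f)/(1 - f)

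- Define f as the assumed false-positive share of recorded teriparatide-arm fractures, with absolute false-positive rates assumed equal across arms.
- Apply the formula to the estimate and the upper confidence bound for f = 5%, 10% and 20%, the last as a stress case.
- Report whether the corrected upper bound stays below 1.3. Since 1.3 x (1 - f) + f is the equivalent observed bound, this means an observed bound below 1.285, 1.27 or 1.24.
- State that f is treated as known, so the corrected interval omits uncertainty in f, and that no correction applies if PPV is equal in both arms.

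Keep the primary decision rule unchanged. The cost is one rewritten sentence and a small calculation on output already planned. The supporting result may be less favourable than the primary one.
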